#### Reporting to the Ethics Committee

The sponsor will assess whether any relevant safety information that becomes available during the study should be reported ad hoc to the EC.

The sponsor has the obligation to, once a year throughout the clinical trial (or on request), submit a progress report to the EC containing an overview of all SARs (Serious Adverse Reactions) occurred during the reporting period and taking into account all new available safety information received during the reporting period.

## 10.3 Data Safety Monitoring Board

Based on the European Medicines Agency (EMA) guidelines on data monitoring committees, the organisation of a Data Safety Monitoring Board is not necessary in the foot drop trial due to following reasons:

1. Peroneal nerve entrapment is no life-threatening disease.
2. The targeted patient population is to be expected to be able to signal any potential harm in an early stage in an appropriate manner.
3. There is no prior knowledge or strong suspicion that a treatment under consideration has the potential to harm patients.
4. The study design gives no reason for setting up a data safety monitoring board
5. The foot drop trial is a study in non-critical indications and both treatment modalities are well characterised, considered daily practice and known for not harming patients.

The independent experts in the TSC will act as an 'extern advisory board' to follow up on possible harm (e.g. related to late cross-over to surgery) and to follow up on blinding and accidental unblinding.

#### 10.4 Notification of deaths

All deaths will be reported without delay to the EC (irrespective of whether the death is related to disease progression, study procedure or is an unrelated event).

# 11 STATISTICS AND DATA ANALYSIS

## 11.1 Sample size calculation

Given that no reliable estimates of the 6MWD are available in this population, the sample size calculation is performed assuming a moderate effect size (mean difference divided by the standard deviation). Based on an effect size of 0.5, 172 patients would have 90% power to show a significant difference at a two-sided significant level of 5% in the change in the 6MWD from baseline to 9 months after randomization using a t-test. The sample size calculation was performed with G\*Power, version 3.1.9.4. To compensate for an expected 5% dropout, a total of 182 patients (91 patients per group) will be included. The expected dropout rate of 5% is based on the results of patients interviews and a large, multicenter, randomised controlled trial comparing surgery versus non-surgery (or delayed surgery) with a design very similar to the foot drop trial (61, 62).

## 11.2 Sample size reassessment

A blinded sample size reassessment by the trial statistician is planned when 50% of the planned patients has reached their 9 month visit or one month before the final patient would be randomized, whichever occurs first. It will be based on the estimation of the overall variance of the primary outcome for the patients for which the primary endpoint data are available and the minimal clinical difference determined from all the patients randomized at that point. The maximum number of patients to be potentially added will be determined before the analysis will take place. It will among others be based on the recruitment rate. Full details of the analysis will be described in an interim analysis plan, which will be finalised after the pilot study and before the analysis will take place. Among others, it will contain the timing, the maximal number of potential extra number of patients to be recruited and the exact methods to be applied. Given that a blind analysis will be performed, the type I error will be preserved and no adjustment to the alpha level for the final analysis will be necessary. The trial will only potentially be extended but never terminated early based on this analysis.

## 11.3 Planned recruitment rate

A recruitment rate and recruitment strategy (table 3 and figure 4) was established for the full-scale study based on the following principles:

- A realistic inclusion rate for pilot study centers was established throughout the pilot study. This was taken into account to estimate a realistic recruitment potential for new centers.
- Based on additional retrospective data analysis in UZ Leuven and the recruitment rate in UZ Leuven during the pilot study, we do not expect any centre to randomize more than 10 patients per year
- All principal investigators were asked to estimate potential recruitment rate based on the number of patients treated in the past and their own experience.
- Centers will be initiated in two phases (see table 3). In a second phase, extra centers can be initiated if recruitment is going slower than expected. In a first phase we would like to start in centers that fulfil following criteria (based on the lessons learned during the pilot study):
  - o Established multidisciplinary collaboration with all disciplines involved
  - o Motivated study team
  - o Centers from Brussels, Flanders and Wallonia
- The possibility of several new COVID-19 pandemic waves should be taken into account. This can slow patient recruitment and site initiating and therefore prolong patient inclusion
- Extra time should be taken into account since a sample size reassessment is planned during the course of the trial

Figure 4 visualises the recruitment strategy for the full-scale study. For every year of the full-scale study, we defined the (expected) maximal recruitment potential based on the estimated recruitment rate of the pilot study centers and phase 1 study centers. We also defined the number of patients that we minimally expect to randomize in the study. If this specific threshold is not reached, we can escalate by initiating the study in the phase 2 study centers. The start of the first year of the trial is defined as the date of the site initiating visit in the last participating phase 1 study centre (for simplicity it has been defined as the year 2023 in figure 5).

**FOOTDROP PHASE 2: 30 patients / year**

Centre	Principal investigator	Estimated recruitment rate / year
PHASE 2 – CENTER 1	XXX	3 -5 PATIENTS PER YEAR
PHASE 2 – CENTER 2	XXX	3-5 PATIENTS PER YEAR
PHASE 2 – CENTER 3	XXX	3-5 PATIENTS PER YEAR
PHASE 2 - CENTER 4	XXX	3-5 PATIENTS PER YEAR
PHASE 2 – CENTER 5	XXX	3-5 PATIENTS PER YEAR
PHASE 2 – CENTER 6	XXX	3-5 PATIENTS PER YEAR

**Table 3 – FOOTDROP study centers**

**Figure 4 – Recruitment strategy**

## 11.4 Statistical analysis plan

### 11.4.1 Analysis sets

The primary analysis will be the full analysis set (FAS) which will include all patients randomized. Patients will be analyzed in the group to which they were randomized, irrespectively which treatment was received, if any. In addition, a per protocol analysis set (PPS) will be used for sensitivity analyses. These will exclude patients or measurements from the FAS with major protocol violations like e.g., receiving surgery for patients randomized to the conservative arm within 9 months after randomization. All major protocol deviations that lead to exclusion from the PPS will be fully documented in the Analysis Sets Specification Document that will be dated and signed prior to database lock.

### 11.4.2 Summary of baseline data and flow of patients

Continuous variables will be summarized by treatment group by the number of non-missing data points, mean, standard deviation, median and interquartile range.

Categorical and ordinal variables will be summarized by treatment group by observed frequencies and percentages relative to the total number of non-missing items.

A CONSORT flow diagram (<http://www.consort-statement.org/>) will be produced to describe the flow of patients (65).

#### **11.4.3 Primary outcome analysis**

The distance covered during the six-minute walk test in meters (6MWD) at 9 months will be evaluated at each visit. A constrained longitudinal data analysis (cLDA) will be performed taking the correlation between these measurements into account. The value at baseline and all follow-up measurements will be taken as responses.

Indicators for baseline, follow-up visits, treatment group and the interaction between follow-up visits and treatment group will be included in the model. Missing data are appropriately taken into account with this model under the missing at random assumption. This is applicable to no-shows (patients that don't show up at study visits). For patients, refusing to participate in the 6MWT, zero as value will be recorded. We do not expect patients to not be able to perform the 6MWT due to peroneal nerve entrapment. All patients should be able to stand and walk a limited distance (if only the foot drop is taking into account). The primary analysis is the comparison between the two treatment groups of the difference in 6MWD between 9 months and baseline.

We will report the mean difference between the two treatment groups with a 95% confidence interval and a two-sided p-value. Superiority of surgery above conservative treatment will be claimed if  $p < 0.05$  and the patients in the surgery arm improved more than the patients in the conservative arm.

Several sensitivity analyses will be performed. The first sensitivity analysis is similar to the primary analysis but with follow-up measurements after surgery not being used in the analysis for patients randomized to conservative treatment but who underwent surgery within 9 months. Similarly, follow-up measurements of patients randomized to surgery who did not undergo surgery will not be used in the analysis. This will allow to estimate the treatment effect most honestly. In the unlikely event that in the conservative treatment arm more than 10% cross-overs are observed, this sensitivity analysis will become the primary analysis and the primary analysis the first sensitivity analysis.

A second sensitivity analysis will be a multiple imputation analysis in which missing follow measurements will be imputed according to the conservative treatment arm for both the surgical and conservative treatment arm.

Full details will be made available in a statistical analysis plan (SAP), which will be finalized before database lock.

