#### 4.3.2 Secondary endpoints

##### Key secondary endpoint: time to recovery.

Very limited data is available regarding time to recovery after surgical or conservative treatment in peroneal nerve entrapment (35, 55). Time to recovery is defined as: the time necessary to cover the minimal age- and sex-specific normal 6MWD AND the time necessary for foot drop recovery to an MRC-score  $\geq 4$  for ankle dorsiflexion. The minimal age- and sex-specific normal 6MWD is defined as 82% of the applied reference equations for prediction of the 6MWD (59, 60). The reference value that will be used is  $6\text{MWD}_{\text{pred}}(\text{m}) = 868.8 - (\text{age}_{\text{years}} \times 2.99) - (\text{gender} \times 74.7)$ . The value for gender is 0 in male subjects and 1 in female subjects (60). The reference values and equation are added to the study protocol in Appendix 5.

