### 8.3 Trial randomisation

Trial randomization is mandatory and affords an unbiased comparison between groups as it controls for both known and unknown variables. Through randomization both the conservative and surgical treated group will be balanced regarding prognostic variables. Both treatment groups will be prognostically balanced (with exception of the intervention), so that if a difference in outcome is observed, a sound argument can be made attributing the difference in result to the intervention under study. Simple randomization based solely on a single, constant 1:1 allocation ratio will be used in the foot drop trial.

The Randomization Module within REDCap will be used to assign participants to specific groups (web-based randomisation/treatment allocation system). In this way, an unpredictable allocation sequence will be generated so that the treatment allocation is concealed from the randomizing treating physician. Randomization will be documented by e-mail. Since peroneal nerve entrapment is not a medical emergency, randomization will not be done outside of the office hours. Randomization will not be stratified by centre because of the risk of selection bias due to treatment predictability in centers with low inclusion rates. Furthermore, due to the anticipated low inclusion rate in several centers, an imbalance in the number of patients per study arm can be created when working with stratification by centre. Therefore, randomization will be global over all participating centers. The PI of the local centre, as well as all the treating physicians, and the study coordinator will receive User Rights for the Randomization Module. The study coordinator should have an overview of all the randomizations made in each centre.

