## 8.6 Baseline data

Baseline data can be collected by the treating physician during the **screening visit** and will be recorded in the eCRF.

- EDX characteristics (see also 8.7.2.)
- Sex (male/female)
- Height in centimetres
- Age in years
- Site of entrapment (left/right/bilateral)
- Time since onset of foot drop in weeks
- MRC score for ankle dorsiflexion and ankle eversion at presentation
- Subacute onset (>2days) of foot drop
- Weight loss during last 6 months:

- Weight loss in kg
  - Current weight
  - BMI (kg/m^2)
  - Is weight loss intentional?
  - Weight loss after bariatric surgery?
  - Rapid onset?
- Postural neuropathy
  - Habitual leg crossing?
  - Prolonged squatting?
  - Frequent kneeling?
- Exercise (dynamic compression)
- Onset after childbirth?
- Previous lumbar surgery?
- Trauma
  - Sharp/blunt
  - Inversion trauma of the ankle
  - Knee dislocation
  - Other
- Iatrogenic causes of peroneal neuropathy
  - Surgery of the hip/knee/ankle
  - Other surgery (e.g. wrong positioning during thoracic surgery)
  - Recent bracing/ pneumatic compression device/ compression wrapping
  - Other
- Metabolic/systemic disease
  - Diabetes mellitus
  - Thyroid disease
  - Vitamin deficiencies e.g. B12
  - Oncological history
  - Other
- Prolonged bedrest
- Professional occupation
- Use of alcohol in units/week
- Tinel sign at the level of the fibular head
- History of neuromuscular diseases
- Professional disability
  - Currently employed/working?
  - Ability to continue working? (last day of work if the patient is unable to work)

**Baseline assessment** for the primary and secondary endpoints analyses will be collected at the **randomisation visit** by the **outcome assessor** (blinded researcher), this will reduce inter-observer variability during follow-up. The limited baseline assessments conducted by the treating physician should be conducted before the actual randomization to avoid bias. The EQ5D-5L is only to be registered if the patient did not complete the online survey or if the patient chose to not use the online system.

Baseline primary and secondary endpoint data will include:

- MRC-score for ankle dorsiflexion, hallux extension and ankle eversion
- Gait assessment:
  - o **Distance covered during the six-minute walk test (primary outcome)**
  - o Gait speed during the 10 meter walk test
  - o Ability to walk barefoot
  - o Stanmore questionnaire
  - o Need for foot-ankle-orthosis
  - o Functional ambulation categories

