## APPENDIX 5. REFERENCE VALUES FOR 6-MINUTE WALK DISTANCE (6MWD) IN A NORMAL HEALTHY POPULATION

### Appendix 5.1. Reference values for 6MWD in a healthy population aged 20 to 80 years

	Subject Age		
	20–40 years	41–60 years	61–80 years
Men			
N	19	12	10
Best 6MWD	800 ± 83 m	*671 ± 56 m	*687 ± 89 m
Women			
N	15	13	10
Best 6MWD	†699 ± 37 m	†670 ± 85 m	583 ± 53 m

SD: standard deviation; WD: walking distance.  
 Group means ± SD. Single factor ANOVA found a significant difference in best 6MWD across age groups in men ( $F = 12.69, P < 0.0001$ ) and in women ( $F = 11.2, P < 0.0002$ ). Post-hoc comparisons using Tukey's test revealed that best 6MWD was significantly greater in younger men than in middle-aged and older men. Post-hoc comparisons using Tukey's test revealed that best 6MWD was significantly lower in older women than in middle-aged and younger women.

\* Significantly different from men aged 20 to 40 years.  
 † Significantly different from women aged 61 to 80 years.

Variable	Coefficient	Cumulative $r^2$	Individual P value
Age (years)	2.99	0.25	<0.0001
Gender	74.7	0.41	<0.0001

WD: walking distance.

The model predicts best 6MWD as:  $868.8 - (2.99 \times \text{Age}) - (74.7 \times \text{gender})$  where men = 0 and women = 1. Although height was significantly related to best 6MWD in univariate regression analysis, it did not improve cumulative  $r^2$  (individual  $P$  value  $< 0.97$ ) when included in the model.

Table 3 \* MULTIPLE LINEAR REGRESSION ANALYSIS OF BEST 6MWD

Reference values for the 6MWD per age-category as published by Gibbons et al. (60).

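### Prespecifying age and sex as covariates in the primary 6MWD model would be a free, probably modest, gain in precision; the planned model is valid without them

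*Protocol*

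**What the plan says.** Protocol section 11.4.3 names a constrained longitudinal data analysis (cLDA) and lists its terms: "Indicators for baseline, follow-up visits, treatment group and the interaction between follow-up visits and treatment group will be included in the model". Baseline is handled inside the model: "The value at baseline and all follow-up measurements will be taken as responses". The contrast is also fixed: "The primary analysis is the comparison between the two treatment groups of the difference in 6MWD between 9 months and baseline". No covariate other than baseline 6MWD appears. The section closes with "Full details will be made available in a statistical analysis plan (SAP), which will be finalized before database lock".

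Elsewhere the protocol treats age and sex as determinants of walking distance:
- Section 8.6 collects both at screening.
- Section 4.3.2 sets the recovery threshold from them: "The minimal age- and sex-specific normal 6MWD is defined as 82% of the applied reference equations for prediction of the 6MWD". The equation is 868.8 - 2.99 × age - 74.7 × (1 if female).
- Section 8.7.5 scales the minimal clinically important difference to the same age- and sex-specific value.
- Appendix 5.1 reports a cumulative r² of 0.41 for age and sex, for the best walk of healthy subjects.
- The subgroup paragraph in section 5.1 lists age above 60 among predictors of outcome, but for exploratory use only.

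Section 8.3 specifies simple 1:1 randomisation without stratification. Section 11.1 sizes the trial on a t-test of change.

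**The concern.** A patient who recovers moves back towards the distance normal for his or her age and sex. The Appendix 5 equation predicts 868.8 - 2.99 × 30 = 779 m for a man of 30 and 868.8 - 2.99 × 70 - 74.7 = 585 m for a woman of 70. Two such patients with the same impaired baseline walk would have different expected walks at 9 months. Because foot drop depresses the baseline walk, baseline 6MWD may not carry all of that difference. Variance that two already recorded variables could explain then stays in the residual, and the confidence interval is somewhat wider than it needs to be.

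This matters a little more than usual here. Section 11.1 says that no reliable 6MWD estimates exist for this population. Section 8.3 says that the arms will be prognostically balanced, but simple randomisation secures that only in expectation. The point is about main-effect adjustment for precision, not about subgroup effects.

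**Working it through.** **1. The plan's own figure.** Section 11.1 gives effect size d = 0.5, two-sided 5%, 90% power, t-test on change. With n per arm the noncentrality is 0.5 × √(n/2). The noncentral t gives 89.99% at n = 85 and 90.3% at n = 86, so 172 in total is right. Allowing for 5% dropout, 172/0.95 = 181.05, which is 182 in two equal arms. The figure reproduces with no covariate.

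**2. What baseline adjustment already gives.** Let ρ be the correlation between baseline and 9-month 6MWD (not in the documents; range assumed), with equal variance σ² at both visits. The variance of change is 2(1 - ρ)σ². The variance at 9 months given baseline is (1 - ρ²)σ². The effective effect size is therefore 0.5 × √(2/(1 + ρ)). This assumes that baseline means are constrained equal between arms, as the name of the method implies.

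| ρ | effective d | power, 86 per arm |
|---|---|---|
| 0.5 | 0.577 | 96.4% |
| 0.7 | 0.542 | 94.3% |
| 0.9 | 0.513 | 91.7% |

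Any gain from age and sex starts from these values, not from 90%.

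**3. What age and sex add, by formula.** Let a0² and a1² be the R² of age and sex with 6MWD at baseline and at 9 months. The share of the variance given baseline that they remove is

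p = (a1 - a0ρ)² / ((1 - ρ²)(1 - a0²)),

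and the standard error is multiplied by √(1 - p). Their share of the variance of change is (a1 - a0)² / (2(1 - ρ)).

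| a0², a1² (assumed) | share of change | p |
|---|---|---|
| 0.41, 0.41 | 0% | 23%, 12%, 8%, 4% at ρ = 0.5, 0.7, 0.8, 0.9 |
| 0.20, 0.20 | 0% | 8% falling to 1% over ρ = 0.5 to 0.9 |
| 0.10-0.20, 0.41 | 4-26% | 26-46% over ρ = 0.5 to 0.8 |

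The gain runs from near nil to material. It depends on whether age and sex predict the 9-month walk better than the baseline walk, which the documents do not show.

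**4. Recovery scenarios.** A simulation ties these quantities to a recovery process. Each patient has a normal distance from the Appendix 5 equation plus a residual, a proportional deficit at baseline, and a proportional recovery by 9 months. Only the equation, the mean age of 55 and the 42% female (the example in section 8.7.5) come from the protocol. Assumed: age SD 12-15, residual SD 75 m, mean deficit 30-40% (patient SD 10-20 points), mean recovery 50-67% (SD 20-35 points), measurement error 20-35 m.

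- Age and sex remove about 4-17% of the 9-month variance given baseline (median 8%). √(1 - 0.04) = 0.98 and √(1 - 0.17) = 0.91, so the standard error is about 2-9% smaller.
- Section 11.4.3 records zero for patients who refuse the walk test. If 3% of walks are zeros (assumed), the share falls to 2-6%. √(1 - 0.02) = 0.99 and √(1 - 0.06) = 0.97, so the standard error is about 1-3% smaller.
- Power rises by roughly 0.5-2.5 points across the scenarios. As one illustration, at ρ = 0.7 and p = 0.08 the effective d goes from 0.542 to 0.542/√0.92 = 0.565, and power from 94.3% to 95.8%.

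**The case against.** The case for leaving the model alone is a serious one.

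- **No error.** Under simple randomisation the unadjusted comparison is valid, no stratification factor has to enter the model, and 182 patients give the stated power. This stands in full.
- **The SAP may add covariates.** Section 11.4.3 defers full details to it, and the SAP is not shown. This stands in part. The section gives a concrete term list, so the protocol can be commented on as written, but the SAP is an acceptable place for the change and may already contain it.
- **The protocol gives a reason.** Section 8.7.5 argues that looking at differences from baseline limits the influence of age and comorbidity. That holds for the effect of age on the level of walking. It does not address the 9-month variance that remains given baseline, so it is an incomplete answer for precision. It does rule out saying that the omission has no rationale.

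Three stronger readings are tempting, and the documents support none of them.

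- A reader might take the r² of 0.41 as the precision lost. It is the share of variance in level among 79 healthy subjects. If age and sex explained 41% of level at both visits, they would explain none of the change.
- A reader might count the gain from 90% power. That figure belongs to the t-test on change; the model already adjusts for baseline.
- A reader might treat chance imbalance as a separate harm. With an assumed age SD of 13 and 42% female, predicted 6MWD has SD √(38.9² + 36.9²) = 53.6 m. The difference between arm means then has SD 53.6 × √(2/91) = 7.9 m, or about ±16 m. But this is imbalance in predicted healthy distance, not in the treatment estimate. Baseline 6MWD absorbs part of it, and the planned confidence interval already reflects the rest.

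**Conclusion.** The point holds as an optional improvement in efficiency. As listed, the primary model omits two recorded variables that the protocol itself uses to predict walking distance, and adjusting for them would probably narrow the confidence interval a little. The likely size is a standard error 2-9% smaller, or 1-3% smaller if some walks are recorded as zero. That is roughly 0.5-2.5 points of power on top of a baseline-adjusted power of about 92-96% (ρ from 0.9 to 0.5). These figures rest on assumed correlations, spreads and recovery patterns; the benefit could be close to nil, or larger if age and sex predict the 9-month walk much better than the baseline walk. Nothing here calls into question the validity of the planned analysis or the sample size.

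**What to change.** In section 11.4.3, or in the SAP before database lock, prespecify age (continuous) and sex as covariates in the primary cLDA, each with its interaction with visit. The predicted 6MWD from the Appendix 5 equation, also with its interaction with visit, is a single-covariate alternative. The visit interaction matters because the argument is that age and sex bear more on the recovered walk than on the impaired one. Report the model without these covariates as supportive.

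The cost is one sentence. Both variables are already collected at screening, so no new data are needed and the sample size does not change.
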